Investigator(s)/Study Center(s):	This study will be conducted at up to approximately 45 study sites in the United States. [REDACTED] will oversee operational aspects of this study on behalf of Semnur Pharmaceutical, Inc., the sponsor of the study.
Phase of Development:	3
Objectives:	
The primary objective of this study is to:
 
 Evaluate the analgesic effect on average leg pain (as measured by the Numeric Pain Rating Scale [NPRS] in the affected leg) following a single transforaminal (TF) injection of SP-102 compared to an intramuscular (IM) injection of placebo over 4 weeks. 
The secondary objectives of the study are to:
 
 Evaluate degree of disability over time as measured by the Oswestry Disability Index (ODI). Characterize the change of the subject's radiculopathy symptoms and overall condition using PainDETECT, Brief Pain Inventory–Short Form (BPI-SF), Clinical Global Impression of Change (CGIC), and Patient Global Impression of Change (PGIC). Evaluate the safety of single and repeat SP-102 TF injections.
Study Design:	
This is a double-blind (DB), randomized, placebo-controlled, multicenter study in subjects with lumbosacral radicular pain evaluating the safety and efficacy of a single SP-102 TF injection compared to a single placebo IM injection, followed by an open-label (OL) safety extension, evaluating an optional repeat SP-102 TF injection, if indicated, administered 4 to 20 weeks later. Subjects will be followed for 24 weeks following the initial treatment (“index injection”).
 
After providing informed consent, each subject will complete a Screening Visit between Day (D) -22 and D-8. Subjects who meet the screening eligibility criteria will record their current, worst, and average pain in their lower back, affected, and non-affected leg using the NPRS scale on a handheld electronic clinical outcome assessment (eCOA) device (ie, "eDiary") twice a day (12 ±2 hours apart) from Screening until Baseline (D1). The 7 days immediately prior to Baseline (D1) will be used to determine eligibility. The average and worst NPRS pain scores will reflect the subject's pain over the last 12 hours. During the screening period, subject's medical eligibility will be also reviewed and confirmed by the study Medical Monitor. Subjects can progress to Baseline (D1) only after medical eligibility approval is provided.
 
Subjects who have been using opioids other than high dose opioids within 30 days prior to Screening (see Exclusion #11), may participate in the study if they agree to discontinue the opioid therapy prior to the Screening Visit and sign the pre-screening informed consent form (ICF).
 
At the Baseline Visit (D1), prior to randomization, the Investigator (or designee) will review the subject's eDiary to determine if the subject meets the eligibility requirements for compliance to continue in the study [REDACTED]
 
[REDACTED] To avoid bias, the investigator and study site staff will remain blinded to the NPRS scores entered in the eDiary by the subject. The eDiary vendor will calculate the NPRS scores and provide the site with a notice of eligibility ([REDACTED])

	
Eligible subjects will then be randomly assigned (in a 1:1 ratio) on D1 to receive a single dose of an SP-102 TF, or placebo [REDACTED] under fluoroscopic guidance. This first injection is referred to as the "index injection". An appropriately trained physician, hereafter called the Injection Physician, administering the DB investigational product (IP) and other assisting staff (eg, nurse) will, therefore, not be blinded to the treatment assignment, while the rest of study staff involved in assessments and collection of data will remain blinded. Procedures will be in place at each site to ensure blinding, minimizing personnel involved with injection, and guarantee sequestration of imaging data acquired at the time of injection.
 
Each subject will have the option of receiving 1 supplemental OL TF injection of SP-102 ("repeat injection"). To qualify for the repeat injection, subjects must meet Repeat Injection Inclusion Criteria, NPRS pain score in the affected leg, and investigator judgment, which includes a safety evaluation demonstrating no signs or symptoms of adrenal suppression or other safety concerns. The repeat injection may be administered between Weeks (W) 4 and 20. Eligible subjects will receive OL SP-102 repeat injection regardless of their initial treatment assignment (SP-102 or placebo).
 
In case of inadequate control of radicular pain, up to 3 g of acetaminophen as rescue medication will be allowed per day. The subject should be instructed to avoid use of acetaminophen in the 6 hours prior to recording an NPRS score. Doses of rescue medication and time taken will be collected in the eDiaries until W12 and thereafter as a concomitant medication.
 
The subject will complete the eDiary twice daily approximately 12 hours apart (± 2 hours) to record their NPRS scores for pain in the previous 12 hours for 12 weeks following index injection. Thereafter, NPRS scores will be recorded at clinic visits.
 
All subjects will be seen at the clinic on D15, and every 4 weeks (ie, W4 [D29], W8 [D57], W12 [D85], W16 [D113], W20 [D141], and W24 [D169]) after the DB index injection for up to 24 weeks. Subjects receiving the OL repeat SP-102 injection will also be seen at the clinic 14 days after the repeat injection and continue the DB planned visits as well. Subjects will also be contacted by telephone by the site staff 2 days after each IP injection to discuss their progress, any medications they are taking, and if they have had any adverse events (AEs).


Planned Sample Size:
	
Approximately 400 subjects will be randomized in this study. The sample size goal of this study is for 332 subjects to complete W4.

Key Subject Selection Criteria:
	
Inclusion Criteria: Screening Visit Inclusion Criteria (D-22 to D-8)
 
 1. Able and willing to read, write, and understand the English language and provide English-language written informed consent prior to beginning any study procedures. 2. Age 18 to 70 years (inclusive) at the Screening Visit. 3. A diagnosis of lumbosacral radicular pain at the Screening Visit. 
[REDACTED]

	
 [REDACTED] [REDACTED] [REDACTED] [REDACTED] [REDACTED] [REDACTED] [REDACTED] [REDACTED] [REDACTED] 
10. If sexually active and a female of childbearing potential or a male capable of bearing a child, agrees to use an effective method of birth control during the study. [REDACTED]
 
 [REDACTED] [REDACTED] [REDACTED] [REDACTED] [REDACTED] 
12. Reviewed all study-specific educational materials and has, in the opinion of the Investigator, the cognitive abilities to understand and appropriately complete all study-mandated procedures.
 
 [REDACTED] [REDACTED]
--	--

	
[REDACTED]
 
[REDACTED]
 
[REDACTED]
 
[REDACTED]
 
[REDACTED]
 
[REDACTED]
 
[REDACTED]
 
[REDACTED]
 
[REDACTED]
 
[REDACTED]
 
[REDACTED]
 
Exclusion Criteria:
 
1. A body mass index $\geq 40 \text{ kg/m}^2$ (without rounding) at the Screening Visit.2. Significant pain unrelated to the disc herniation that, in the Investigator's and/or Sponsor's opinion, would significantly compromise assessment of the radicular back and leg pain related to the disc herniation.[REDACTED][REDACTED][REDACTED][REDACTED][REDACTED][REDACTED][REDACTED][REDACTED][REDACTED][REDACTED][REDACTED][REDACTED][REDACTED][REDACTED][REDACTED]10. Chronic use (ie, up to 6 consecutive days) of oral or parenteral steroid medication during the 2 months prior to the Screening Visit.11. Regular use of high dose opioids (> 30 mg morphine equivalents for more than 2 days per week) in the 30 days prior to the Screening Visit. The subject must agree to discontinue all opioids prior to the Screening Visit.12. Cannot stop use of neuro stimulator for pain control on or before Screening Visit and for the duration of study participation.13. Cannot interrupt chronic long-acting anticoagulant therapy before index or repeat injection.14. History of Insulin-dependent Diabetes Mellitus.
--	--

	
15. History of diabetic neuropathy or peripheral neuropathy other than radiculopathy in the lower extremities.
 
16. History of malignancy or evidence of malignancy, lymphoproliferative, or neoplastic disease except for successfully treated basal or squamous cell carcinoma of the skin or cervical intraepithelial neoplasia within 5 years of the Screening Visit.
 
17. Anxiety or depression based on Hospital Anxiety and Depression Scale scores ≥ 15 at Screening Visit, or has a major psychiatric disorder not controlled with medication that would interfere with clinical pain scores or participation in the trial.
 
18. Known history of any clinically significant or unstable medical condition including disorders of glucocorticoid regulation (eg, Cushing's or pseudo-Cushing's disease, adrenocortical insufficiency), any other disorder, condition or circumstance (including secondary gain) that in the opinion of the Investigator has the potential to prevent study completion and/or to have a confounding effect on outcome assessments.
 
19. Alcohol dependence, illicit drug use based on urine screen, drug abuse, or drug addiction within 1 year of the Screening Visit.
 
20. Clinically significant abnormalities that may interfere with participation in the trial such as:
 
■ [REDACTED]■ [REDACTED]■ [REDACTED]■ [REDACTED] 
[REDACTED]
 
22. Use of any investigational drug and/or device within 30 days prior to the Screening Visit or is scheduled to receive an investigational drug other than blinded study drug during this study.
 
23. If female, are lactating/breastfeeding, plan to breastfeed, or plan to become pregnant while participating in the study.
 
[REDACTED]

Study Drug(s):
	
Investigational Product: SP-102 drug product is comprised of [REDACTED]
 
[REDACTED]
 
The drug product is a sterile [REDACTED]
 
[REDACTED] which is intended to be delivered via a TF injection, using 6-inch long microbore/small bore extension tubing.
 
Placebo control: [REDACTED]
 
[REDACTED]

	All IP will be packaged in 
Duration of Treatment:	One or 2 doses of IP separated by 4 to 20 weeks. Subjects will be followed for 24 weeks after the index injection.
Main Parameters of Efficacy:	
Efficacy assessments include:
 
 • NPRS recorded in the eDiary twice daily approximately 12 hours apart ± 2 hours: 
 ○ The NPRS worst pain score in the affected leg ○ The NPRS average pain score in the affected leg • NPRS recorded at each study visit: 
 ○ The NPRS current pain score in the affected leg ○ The NPRS average pain score in the lower back • ODI • PainDETECT • BPI-SF • PGIC • CGIC • Use of rescue medication (acetaminophen) as captured in the eDiary
Main Parameters of Safety:	
 • Physical examination • General Neurological Exam • Targeted Neurological Exam • Vital signs (blood pressure and heart rate) • Electrocardiogram • Laboratory parameters (serum chemistry, hematology, and urinalysis) • AEs
Efficacy Endpoints:	
The primary efficacy endpoint is:
 
 • The mean change from Baseline (D1) to W4 in the mean NPRS average pain score in the affected leg 
The key secondary efficacy endpoint is:
 
 • The change in ODI total score from Baseline (D1) to W4. 
Other secondary endpoints are:
 
 • The time to repeat injection of SP-102 from index injection. • Proportion of subjects receiving repeat injection. • The mean change from Baseline (D1) to W2, W8, and W12, in the mean NPRS average pain score in the affected leg. • The mean change from Baseline (D1) to W2, W4, W8, and W12, in the mean NPRS worst pain in the affected leg. • The mean change from Baseline (D1) to W2, W4, W8, and W12 in the mean NPRS current pain score in the affected leg. • The mean change from Baseline (D1) in the ODI total score to W12. • The mean change in PainDETECT from Baseline (D1) to W4 and W12. • The mean change in BPI-SF score from Baseline (D1) to W4 and W12.

	
• Proportion of subjects achieving a response of 30%, 50%, and 75% reductions from Baseline (D1) in mean NPRS average pain score in the affected leg at W2 and W4.• The mean change from Baseline (D1) to W2, W4, W8, and W12 in the mean NPRS average pain score in the lower back.• PGIC at W2, W4, W8, and W12.• CGIC at W2, W4, W8, and W12.• Cumulative use of rescue medication (mg of acetaminophen) through W4 and W12.• Time to first rescue medication dose.• Proportion of subjects requiring rescue medications.
Safety Endpoints:	
• AEs, compared between 4 groups receiving 1 SP-102 injection, 2 SP-102 injections, placebo followed by SP-102 repeat injection, or placebo only.• Change from Baseline (D1) in laboratory parameters.• Change from Baseline (D1) in vital signs.• Change from Baseline (D1) in neurological examination.
Statistical Analyses:	 The content of this table cell is completely redacted with black boxes.

	
[REDACTED]
 
Safety summaries will be provided for proportion of subjects experiencing AEs, clinical laboratory evaluations, vital sign measurements, and neurological examinations.
 
No interim analysis is planned for this study. Note that the study will be unblinded and the primary analysis will be completed after all subjects complete the 12-week assessments and data are cleaned. Subjects in the OL safety extension portion of the study will continue through W24. No efficacy data in the first 12 weeks of the study will change after the primary analysis is completed.

--	--

TABLE OF CONTENTS

SIGNATURE PAGE	2
SUMMARY OF CHANGES incorporated with AMENDMENT 3	3
SUMMARY OF CHANGES incorporated with AMENDMENT 2	4
SUMMARY OF CHANGES incorporated with AMENDMENT 1	5
SYNOPSIS.....	6
TABLE OF CONTENTS.....	14
LIST OF ABBREVIATIONS AND DEFINITIONS OF TERMS.....	19
1 INTRODUCTION	23
1.1 Background.....	23
1.1.1 Lumbosacral Radicular Pain.....	23
[REDACTED].....	
1.1.3 SP-102.....	25
1.2 Preclinical Studies.....	25
1.3 Clinical Studies.....	26
[REDACTED].....	
1.5 Study Rationale.....	27
1.6 Dose Rationale.....	27
1.7 Study Endpoint Rationale.....	28
1.8 Risks and Benefits for Subjects	28
2 STUDY OBJECTIVES.....	30
2.1 Primary Objective	30
2.2 Secondary Objectives.....	30
3 INVESTIGATIONAL PLAN.....	31
3.1 Overall Study Design and Plan.....	31
3.2 Study Duration.....	33
3.3 Selection of Study Population.....	33
3.3.1 Inclusion Criteria	33

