3.4.8.2 Prior and Concomitant Medications

All prescription and non-prescription medications (eg, over-the-counter drugs and herbal supplements) that subjects report taking during the 30 days prior to the Screening Visit will be assessed and recorded in the eCRF Concomitant Medication. For each medication, documentation should list the trade or generic name, the total daily dose including units (or the dose, units and scheduled and actual frequency of administration if the medication is not taken daily), the route of administration, and the reason for use.

Concomitant medication refers to all drugs and therapies used from the time of informed consent through the EOS participation. For D1 to Week 12, rescue medication (acetaminophen) use will be recorded only in the eDiary by the subject. After W12, when the eDiary is returned to the clinic, subjects will report acetaminophen use to study staff, and reported use will be documented in the Concomitant Medication eCRF.

[Redacted]

Changes, additions, or discontinuations to medications will be assessed and recorded in the eCRF during each study visit and at the EOS/ET Visit (D169). All as needed (*pro re nata*, *PRN*) prescriptions should be converted to reflect actual number of pills and dose taken per day.

To be eligible for this study, each subject agrees that any oral, non-opioid analgesic medication regimen for or indications other than radiculopathy pain (eg, neuropathic pain, cardiac prophylaxis) will not be altered from the Screening Visit through W12. The Investigator must inform the Medical Monitor (in advance, if possible) if a subject requires analgesic medications contrary to the protocol during the study.

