Hematology: Hemoglobin, hematocrit, red blood cell count, WBC count (with differential [lymphocytes, neutrophils, eosinophils, basophils, and monocytes]), and platelet count.

Blood Chemistry: albumin, alkaline phosphatase, AST, ALT, direct bilirubin, total bilirubin, blood urea nitrogen, calcium, chloride, creatine kinase (Screening only), creatinine, gamma-glutamyl transferase, glucose, lactate dehydrogenase, potassium, sodium, and uric acid.

Other tests: HbA1c, HIV, hepatitis B, and hepatitis C at Screening. Coagulation tests at Screening: activated PTT, PT, and INR. Coagulation tests may be repeated prior to the index and repeat injection, if deemed necessary by the Investigator.

Urinalysis: Dipstick analysis: color, turbidity, specific gravity, pH, glucose, protein, ketones, urobilinogen, bilirubin, blood nitrate, leukocyte esterase, and microscopic examination when indicated by dipstick results.

Urine drug screen: Includes opiates, barbiturates, benzodiazepines, tricyclic antidepressants, cannabinoids, PCP, cocaine, ecstasy, and amphetamines. A urine drug screen will be obtained at Screening, Baseline (D1), W2, and W4. A urine drug screen may be repeated if deemed necessary by the Investigator.

For females of childbearing potential: Serum pregnancy test at Screening. Urine pregnancy test at Baseline (D1) and at Repeat Injection. A urine pregnancy test may be repeated if deemed necessary by the Investigator.

Laboratory samples will be analyzed by a central laboratory [REDACTED] to ensure consistent interpretation of results. Samples are to be shipped to [REDACTED], [REDACTED]. In the event of an unexplained clinically noteworthy abnormal laboratory test value, the test should be repeated immediately and followed up until it has returned to the normal range and/or an adequate explanation of the abnormality is found.

3.5.7.6 Adverse Events:

All AEs occurring after the subject signs the ICF through W24, D169 will be recorded. See [Section 4](#) for additional information.

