- **PainDETECT:** PainDETECT is a 7-question validated tool to determine the prevalence of neuropathic pain in individuals with lower back pain. The 7 responses are summed for a possible score ranging from 0-35. In addition to the 7 questions, subjects note the course of pain (Persistent pain with slight fluctuations; Persistent pain with pain attacks, Pain attacks without pain between them; Pain attacks with pain between them; and Radiating pains marked on a body chart) for a total, overall scale score of 0-38. PainDETECT will be collected at Screening, Baseline (D1), W4, W12, and W24.
- **BPI-SF:** The BPI assesses pain at its "worst," "least," "average," and "now" (current pain). The pain severity domain will be derived by summing items 3-6.

The BPI also measures how much pain has interfered with 7 daily activities, including general activity, walking, work, mood, enjoyment of life, relations with others, and sleep. BPI pain interference is typically scored as the mean of the 7 interference items. The pain interference domain will be derived by summing items 9A - 9G.

- **Rescue Medication:** In this study, acetaminophen is the permitted and study provided rescue medication. The time to first rescue medication dose and number of mg taken will be collected and analyzed.

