#### **7.12.6.13 Cumulative use of rescue medication (mg of acetaminophen)**

In this study, acetaminophen is the permitted and study-provided rescue medication. For subjects that withdraw early, their missing weekly values after withdrawal will be imputed using the average weekly score for the respective treatment group. If the subject has partial records of rescue medication on the week of subject's withdrawal, the rescue medication use on that week will be imputed as follows:

[ partial record of rescue medication on the withdrawal week \* (7/number of days in the withdrawal week with partial record) ].

Cumulative use of rescue medication at Week 4 will be obtained as the rescue medication use during the first four weeks relative to the index injection, that is, up to the subject's Day 29 in the study. It will be analyzed using an analysis of variance (ANOVA) model with cumulative use from baseline to Week 4 as the response variable with fixed effects for treatment (two groups: SP102 or placebo), site, and Pain Catastrophizing Scale group ( $<30$  or  $\geq 30$ ). The same ANOVA model will

be applied on only subjects that complete 4 Weeks and output will be presented using the two treatment groups.

Cumulative use of rescue medication at Week 12 will be obtained as the rescue medication use during the first 12 weeks relative to the index injection, that is, up to subject's Day 85 in the study. It will also be analyzed using an ANOVA model with cumulative use from baseline to Week 12 as the response variable with fixed effects using the four treatment (SP-102/SP-102, PBO/SP-102, SP-102/none, PBO/none) variable, site, and Pain Catastrophizing Scale group (<30 or ≥30). The same ANOVA model will be applied on only subjects that complete 12 Weeks and output will be presented using the four treatment groups.

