#### **7.12.6.14 Time to first rescue medication dose**

The time to first rescue medication dose, in days, will be analyzed like the time to event endpoint in [Section 7.11.6.2](#). Time to first rescue medication dose will be analyzed separately for the first 4 weeks (two groups), and the first 12 weeks (four groups). For both analysis periods, time to first rescue medication dose will be calculated relative to the date of index injection. For the primary analysis period (first 4 weeks), subjects who do not use rescue medications for the first 4 weeks will be censored at Day 29th while subjects who discontinue the study prior to the subject's Day 29th in the study will be censored at the time of discontinuation. Similarly, for the secondary analysis period, subjects who do not use rescue medication for the first 12 weeks will be censored at Day 85th while subjects who discontinue the study prior to the subject's Day 85th in the study will be censored at the time of discontinuation.

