### 7.13.2 Laboratory Data

Descriptive statistics of the observed values and change from baseline (continuous data) will be presented by treatment group and visit for each hematology (hemoglobin, hematocrit, red blood cell count, white blood cell (WBC) count (with differential [lymphocytes, neutrophils, eosinophils, basophils, and monocytes]), platelet count, hemoglobin A1c, activated partial thromboplastin time, prothrombin time and international normalization ratio), urinalysis (color, turbidity, specific gravity, pH, glucose, protein, ketones, urobilinogen, bilirubin, blood nitrate, leukocyte esterase, and microscopic examination) and serum chemistry (albumin, alanine aminotransferase [ALT], alkaline phosphatase, aspartate aminotransferase [AST], direct bilirubin, total bilirubin, blood urea nitrogen, calcium, chloride, creatine kinase, creatinine, gamma-glutamyl transferase, glucose, lactate dehydrogenase, potassium, sodium, uric acid) parameter. Each measurement (continuous data) will be classed as below, within, or above normal range, based on ranges supplied by the laboratory used. Laboratory data will be summarized for the secondary analysis period.

Shift tables in relation to the normal range from baseline to each follow-up visit will be presented.

All other laboratory tests will be listed only. This includes troponin I, troponin T, lipid panel, plasma cortisol, human immunodeficiency virus (HIV), hepatitis B, hepatitis C, and serum

pregnancy test (females of childbearing potential only), cortisol, urine drug screen, and urine pregnancy test.

A listing of abnormal laboratory measurements defined as any out of normal range laboratory values recorded throughout the study will be presented.

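### Three rescue endpoints count only eDiary acetaminophen, so a retained subject who takes a different analgesic for radicular pain and no acetaminophen is scored as rescue-free

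*Protocol*

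**What the plan says.** **Definition.** Among the main efficacy parameters, the protocol synopsis lists "Use of rescue medication (acetaminophen) as captured in the eDiary". Protocol 5.2.8 states that "In this study, acetaminophen is the permitted and study provided rescue medication", and SAP 7.12.6.13 says the same. Protocol 3.4.8.2 adds that, from D1 to Week 12, "rescue medication (acetaminophen) use will be recorded only in the eDiary by the subject".

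**Scoring.** For time to first rescue dose, SAP 7.12.6.14 says that "subjects who do not use rescue medications for the first 4 weeks will be censored at Day 29"; the 12-week analysis uses Day 85 in the same way. SAP 7.12.6.15 compares the proportion requiring rescue by chi-square test. SAP 7.12.6.16 divides days without rescue medication by 28. The wording of these sections shows no redaction, and none of them mentions any other analgesic.

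**Other analgesics.** Protocol 3.4.8.2 tells the investigator to inform the Medical Monitor "if a subject requires analgesic medications contrary to the protocol during the study". It has other drugs recorded in the concomitant-medication eCRF with dose, route and reason for use. SAP 7.9 summarizes coded concomitant medications at ATC Level 2, including a first-four-weeks table by randomized arm. Protocol 3.5.7.5 says "A urine drug screen will be obtained at Screening, Baseline (D1), W2, and W4", with opiates on the panel. SAP 7.13.2 places "cortisol, urine drug screen, and urine pregnancy test" among the results that are listed only.

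**Populations.** SAP 7.12.6 analyses these endpoints in both mITT and PP. SAP 7.2.3 makes mITT primary for efficacy.

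**The concern.** Endpoints named for needing rescue, or for days free of it, will be read as measures of pain control. A subject whose pain is poorly controlled and who takes an NSAID or an opioid instead of the study-provided acetaminophen looks, on these three endpoints, the same as a subject who needed nothing. If that happens more often in one arm, the comparison shifts in that arm's favour. If it is more common on placebo, an SP-102 benefit shrinks or reverses. If it is more common on SP-102, a benefit is enlarged or created. The endpoints belong to the other-secondary family, to which SAP 7.12.6.19 applies sequential testing.

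**Working it through.** The documents state no figure for this point, and the sample size section is redacted, so there is nothing to reproduce. The check has two parts.

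**1. Scoring one subject under the SAP rules.** Take a subject followed to Day 29 who takes no acetaminophen and uses another analgesic for radicular pain on k of 28 days.

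| Endpoint | As written, any k | If such use counted |
|---|---|---|
| Time to first rescue (7.12.6.14) | censored at Day 29 | event at first use |
| Requiring rescue (7.12.6.15) | no | yes |
| Rescue-free days (7.12.6.16) | 28/28 = 100% | (28 − k)/28: 75% (k = 7), 50% (k = 14), 0% (k = 28) |

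Each entry in the middle column is the most favourable value available. Cumulative use (7.12.6.13) is 0 mg for the same subject, but that endpoint is expressed in mg of acetaminophen and does what its name says.

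Two variants score differently:
- One acetaminophen dose makes the subject an event for time to first rescue and for the proportion. Days on the other drug alone still count as free.
- A subject who withdraws before Day 29 is censored at discontinuation, so does not get the longest time. Percent free days is still 100% up to the termination date.

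**2. Scale, on assumed rates.** Let P and A be the true proportions on placebo and SP-102 that use any analgesic for this pain by Day 29. Let s_P and s_A be the proportions that use only something other than acetaminophen. The scored proportions are P − s_P and A − s_A, so the scored difference (placebo minus SP-102) is (P − A) − (s_P − s_A). Only the imbalance s_P − s_A shifts the difference.

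Inputs: n = 166 per arm (332 Week 4 completers in the synopsis, randomized 1:1, 332/2) and two-sided 5% (SAP 7.12). All rates are assumptions. Power is Φ((|d| − 1.96·SE0)/SE1), where SE0 is the pooled and SE1 the unpooled standard error. With true rates of 70% and 55%, d = 0.15, SE0 = √(2 × 0.625 × 0.375/166) = 0.0531 and SE1 = √((0.21 + 0.2475)/166) = 0.0525. This gives z = 0.87 and power 0.81.

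| s_P | s_A | Scored placebo vs SP-102 | Difference (points) | Power |
|---|---|---|---|---|
| 0 | 0 | 70% vs 55% | 15 | 0.81 |
| 5% | 0 | 65% vs 55% | 10 | 0.46 |
| 10% | 0 | 60% vs 55% | 5 | 0.15 |
| 10% | 5% | 60% vs 50% | 10 | 0.45 |
| 10% | 10% | 60% vs 45% | 15 | 0.78 |
| 0 | 5% | 70% vs 50% | 20 | true difference is 15 |

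With no true difference (60% in both arms), s_P = 10% and s_A = 0 give scored rates of 50% and 60%, a false 10-point difference against SP-102. Equal use of other drugs does almost no harm; unequal use can do a good deal. The documents do not say which applies.

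**The case against.** **The endpoint is acetaminophen rescue by design.** The documents name one rescue drug and treat other analgesics as contrary to the protocol, so an any-analgesic endpoint is a different construct. This stands in part: the plan does not contradict itself, and the acetaminophen-only result should stay visible. It does not remove the problem that endpoints about needing rescue give their best values to someone who needed another drug.

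**The plan already handles it elsewhere.** PP excludes major deviators, decided before unblinding, and the first-four-weeks medication table could show an imbalance between arms. Both are useful. But the deviation categories are redacted, so whether PP removes these subjects cannot be seen, and neither step alters the mITT rescue endpoints.

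**A rule may sit in redacted text.** Protocol 3.4.7, 3.4.8.3, 3.4.9, 3.5.7.7, 5.2.4 and 5.2.8.4 have no usable visible text. This stands, and absence is claimed only for what can be read. An any-analgesic rule there would conflict with the acetaminophen-only wording in the synopsis, protocol 5.2.8 and the SAP.

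**The sequential test may never reach these endpoints.** The order in SAP 7.12.6.19 is redacted. If it follows the list in SAP 4.3 after the primary and key secondary, these three are 16th to 18th. This limits the consequence for formal claims, but not for the descriptive reading of the results.

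**Counting other analgesics brings in a date bias.** SAP 7.3.5 sets a missing start date to the index injection date when the drug is ongoing or stopped on or after injection. It does the same when only the day is missing and the month is that of the injection. Used as it stands, it would create false Day 1 rescue events. This is correct, and the fix has to deal with it.

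**Conclusion.** The point holds on the visible text for the mITT analysis, for a subject who stays in follow-up, takes no acetaminophen and uses another analgesic for back, leg or radicular pain. The mis-scoring follows from the rules; its frequency, size and direction do not. It is a worthwhile correction to other-secondary endpoints.

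A reader might infer three stronger things that the documents do not support:
- **That the protocol expects subjects to turn to other analgesics.** The text in 3.4.8.2 is a contingency clause. Protocol 3.1 admits subjects who stop opioids below the high-dose threshold before Screening, which makes such use conceivable but gives no rate.
- **That the rescue results will be biased in a known direction or by a known amount.** Every rate in the illustration is assumed, and equal use in both arms leaves the difference unchanged.
- **That the efficacy conclusion is at risk.** The primary NPRS and key secondary ODI endpoints do not use rescue data in this way.

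**What to change.** In SAP 7.12.6.14 and 7.12.6.15, define the event as the earlier of an eDiary acetaminophen dose and an analgesic newly started or increased after the index injection for back, leg or radicular pain. In 7.12.6.16, count a day with either as not rescue-free.

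- **Source.** Identify the other analgesics from the coded concomitant-medication eCRF, using reason for use, by blinded review completed before unblinding. SAP 7.12.3 already classifies opioids by ATC code and compares medication dates for a baseline factor, so the method is familiar to the plan.
- **Dates.** State a separate rule: the SAP 7.3.5 imputation to the index injection date is not used for these events. Settle missing or partial start dates in the blinded review, and show results with undated cases both counted and not counted.
- **Reporting.** Give acetaminophen-only results alongside, leave cumulative mg unchanged, and show the number of other-analgesic users by arm.
- **Urine screens.** Use the Week 2 and Week 4 opiate results only as a consistency check, since they cannot date use and do not detect NSAIDs.

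The cost is SAP wording, one blinded medication review and some residual uncertainty about start dates. Nothing changes in which drugs are allowed or how subjects are managed. Settled before unblinding, the rule is pre-specified; settled afterwards, it would be a post-hoc choice.
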